### **8.5.2. Study Termination Criteria**

Study termination refers to a patient's stopping study follow-up, which includes study assessments, visits, and all contact with the site regarding the trial. Reasons for study termination include the following:

- Death;
- Lost to follow-up;

- Withdrawal of consent by patient.

Every reasonable effort should be made to contact patients who do not return for a scheduled visit. Follow-up options described in Section 8.5.1 should be discussed, as soon as possible, with patients who no longer wish to return for all scheduled in-person visits, patients who have failed to return for a scheduled visit, and patients who may be demonstrating an increasing risk of no longer communicating with the site. Patients should not be considered lost to follow-up until the scheduled Week 112 visit date.

The term “withdrawal of consent” should be used only when the patient no longer wishes to participate in the trial and no longer authorizes investigators to make efforts to continue to obtain their outcome data. Unless the patient provides written withdrawal of consent or there is other written documentation by the investigator confirming the patient’s verbal intent to completely withdraw from the trial, patients should be followed for all protocol specified evaluations and assessments. The investigator should inquire about the reason for withdrawal of consent, request the patient return all unused investigational product, request the patient return for end-of-treatment and follow-up visits (if applicable), and follow-up with the patient regarding any unresolved AEs. Withdrawal of consent is a critical trial event and therefore should be approached with the same degree of importance and care as is used in initially obtaining informed consent or assent, if applicable. The reasons for a patient’s intended withdrawal need to be completely understood, documented, and managed to protect the rights of the patient and the integrity of the trial. Only patients who withdraw permission for all follow-up options outlined in Section 8.5.1 are considered to have completely withdrawn their consent to participate in the study.

## **9. TREATMENT OF PATIENTS**

### **9.1. Select Management Guidelines**

The guidelines below apply to the management of study participants.

#### **9.1.1. Management of Fluid Status**

Specific risk mitigation procedures will be employed to reduce the potential for bardoxolone methyl-induced fluid overload. These procedures include exclusion of patients with any severe renal disease, defined as an eGFR value of  $< 30 \text{ mL/min/1.73 m}^2$ . To exclude patients with significant cardiac dysfunction, the study will exclude patients with a history of left-sided heart disease. Patients who have evidence of volume overload at baseline, defined as BNP level of  $> 200 \text{ pg/mL}$ , will also be excluded.

Laboratory data and rapid weight gain will also be used to monitor fluid status after randomization. Patients who experience a BNP  $> 100 \text{ pg/mL}$  that represents a doubling (or more) of BNP levels from Day 1 should have an unscheduled telephone contact immediately to evaluate for any symptoms of fluid overload, and accordingly, request an unscheduled visit to assess signs and symptoms of congestive heart failure, heart failure, acute pulmonary edema, etc. identified through the telephone contact. In addition, patients will be given a Sponsor-provided scale to use at home to collect and record weights daily during the study. In the event the Sponsor-provided scale is temporarily unavailable (e.g., patient is traveling, replacement scale has not arrived to patient, etc.), patients may use any available scale. Use of a scale other than the Sponsor-provided scale should be documented in the patient diary. Patients who experience a weight increase of three pounds (1.4 kilograms) in a day or five pounds (2.3 kilograms) or greater increase within a week must have an unscheduled telephone contact immediately. Whether prompted by BNP elevations, sudden weight gain, or by the presence of clinical signs and symptoms the patient must be instructed to stop taking their study medication immediately and be medically evaluated by the investigator or a local physician within 1 to 2 days.

Investigators are encouraged to consider starting or increasing doses of diuretics (thiazides, loop diuretics) early after recognition of edema. This can be done concurrently with temporary discontinuation of the study drug. Patients may not restart their study medication until the investigator has completed and documented an assessment of fluid overload.

Investigators should advise patients to watch for signs and symptoms of fluid overload. Patients should be informed to notify their physicians immediately if they experience swollen feet, chest pain, shortness of breath with mild exertion or while lying down, or other relevant symptoms. The investigator must immediately assess symptoms of fluid overload and determine appropriate medical management, as necessary, including whether stopping drug administration is required.

#### **9.1.2. Management of Elevated Transaminase Levels (ALT and/or AST)**

For only patients who enrolled under Version 2 of the protocol (only performed in the US at the beginning of the study) and are receiving tolvaptan (JYNARQUE), liver biochemistries (ALT, AST, and/or bilirubin levels) should be monitored according to the relevant package insert/REMS program for tolvaptan.

For all patients enrolled, nearly all instances of elevated transaminases due to bardoxolone methyl treatment are expected to be asymptomatic.

Some patients may experience more rapid increases in ALT/AST values than others during the dose titration period. Investigators may consider extending the time between each dose increase to manage ALT/AST elevations.

If a patient's transaminases are elevated, follow the instructions outlined in Table 5.

**Table 5: Management of Elevated Transaminase Levels (ALT and/or AST)**

ALT and/or AST Level(s)	Interrupt Dose?	Procedure
> 8x ULN	Yes	
 
➤ Discontinue study drug temporarily
 
➤ Contact the Medical Monitor
 
 
Study drug may be restarted with Sponsor approval after all the following criteria are met:
 
 
• Ultrasound or MRI of the hepatobiliary tree*;
 
• ALT and AST returned to <math>\leq</math> ULN;
 
• TBL is within normal range;
 
• Other relevant labs (e.g., albumin, INR, PT) are within normal range;
 
• No clinical signs or symptoms of liver injury are present.
 
 
*Based on imaging results, if additional tests/studies are warranted, this should be discussed with the Medical Monitor.

> 5x ULN for more than 2 weeks		
> 3x ULN with appearance of fatigue, nausea, vomiting, right upper quadrant pain or tenderness, fever, rash, and/or eosinophilia		
> 3x ULN and (TBL > 2X ULN or INR > 1.5)		
> 3x ULN	No	
 
➤ Check transaminase levels (as well as TBL, GGT, ALP, and INR) within 48 to 72 hours
 
 
Continue testing for ALT/AST every 72 to 96 hours until transaminase levels are below 3X the ULN for at least one week

ALP = alkaline phosphatase, ALT = alanine aminotransferase, AST = aspartate aminotransferase, GGT = gamma-glutamyl transpeptidase, INR = international normalized ratio, MRI = magnetic resonance imaging, PT = Prothrombin Time, TBL = total bilirubin, ULN = upper limit of normal
		

Patients who meet the interruption criteria outlined above must restart study drug at the 5 mg dose level and dose titrate according to Section 7.3.3.

### 9.1.3. Management of Muscle Spasms

Basic symptomatic relief is the first step in managing muscle spasm, including walking, adequate hydration, wearing socks, and stretching before bedtime. Assessment of levels of electrolytes such as magnesium, calcium, and potassium may indicate the need for replacement. Serum vitamin D levels may be collected by the investigator, in the evaluation of muscle spasms. If vitamin D levels are low, supplementation may be warranted. Muscle relaxants may also help relieve symptoms.

### 9.1.4. Weight Loss

**Adults** - The investigator should evaluate a patient for unexplained weight loss of 7% or greater from the Day 1 weight. Ongoing assessments of other symptomology (for example: nausea, vomiting, abdominal pain or poor appetite) may be warranted to ensure the patient is receiving adequate nutrition and evaluate for other causes of weight loss.

**Adolescents** - If weight loss of greater than 5% from the Day 1 weight is observed, the investigator should temporarily stop study drug, and evaluate the patient for any symptomology (for example: nausea, vomiting, abdominal pain or poor appetite) leading to weight loss, and/or other causes of weight loss. The investigator should inform the Medical Monitor prior to stopping study drug, and the investigator and Medical Monitor should discuss management of the patient.

### 9.1.5. Hypomagnesaemia

In instances where a patient experiences hypomagnesaemia, defined as serum magnesium less than 1.3 mEq/L (0.65 mmol/L), consideration should be given for repletion of serum magnesium.

### 9.1.6. Management of Urinary Protein

Although increases in urinary protein with bardoxolone methyl have not been associated with renal injury or loss of kidney function, investigators should closely monitor patients if urinary albumin to creatinine ratios increase by more than 100% and exceed 1000 mg/g for proteinuria and should consult the Medical Monitor for appropriate measures.

### 9.1.7. Management of Blood Pressure

Investigators should attempt to maintain the blood pressure within the range recommended by the Kidney Disease Blood Pressure Working Group (KDIGO):  $\leq 140$  mm Hg systolic and  $\leq 90$  mm Hg diastolic for patients with urine albumin to creatinine ratio (ACR)  $< 30$  mg/g, and  $\leq 130$  mm Hg systolic and  $\leq 80$  mmHg diastolic for patients with ACR  $> 30$  mg/g (KDIGO, 2012).

Patients being treated with an ACE inhibitor and/or ARB should be receiving the maximally tolerated labeled daily dose (MTLDD), defined as the dose at or below the labeled dose that does not exhibit any intolerable adverse effects (e.g., hypotension, hyperkalemia), based on the investigator's assessment. If the patient is currently receiving one drug (ACE inhibitor or ARB) below the maximum labeled dose, the drug should be titrated to the MTLDD based on the assessment of tolerability by the investigator at least 6 weeks prior to the Screen A visit. Diuretics may be titrated to help maintain blood pressure target levels.

Any changes in ACE inhibitor or ARB use or diuretic therapy should be preceded by consideration of any relevant contraindications as per the local product information.

### 9.1.8. Nausea

Nausea may occur with higher doses of bardoxolone methyl. Nausea AEs are typically mild and reversible within a few weeks after treatment initiation. If symptoms do not resolve, dose de-escalation, with consultation of the Medical Monitor, may be reasonable.

### 9.1.9. End Stage Kidney Disease

Patients approaching end stage kidney disease (ESKD) should be closely monitored by the investigator to fully characterize their progression. For patients with eGFR  $\leq 15.0$  mL/min/1.73 m^2 (as calculated by the site, using the central lab-provided serum creatinine and the formulas provided in Section 9.10.18.1), initiate more frequent follow-up to closely monitor safety assessments (i.e., clinical chemistry (incl. eGFR), hematology, vital sign assessments (incl. weight), BNP and NT-proBNP). Similar frequent follow-up may also be implemented for patients with eGFR  $> 15.0$  mL/min/1.73 m^2 who, in the investigator's opinion based on the anticipated progression of their disease, may be approaching ESKD. Patient follow-up should be completed in-person or through a home health visit where in-person visits are not feasible, at least once every 4 weeks ( $\pm 2$  weeks), until one of the following occurs:

- Initiation of dialysis;
- Receipt of transplant.

Two off-treatment serum creatinine assessments should be collected 28 to 36 days after last dose, and prior to initiation of dialysis or receipt of transplant. Upon initiation of dialysis, study drug should be interrupted. Because laboratory and vital sign assessments can be affected by receiving dialysis, those safety assessments should not be performed concurrently while a patient is receiving dialysis. Patients receiving dialysis should continue to be followed for vital status and SAEs by phone or in-person according to the protocol scheduled visits. Dialysis not lasting at least 12 weeks will be considered acute dialysis, and patients should be considered for re-initiation of study drug with Medical Monitor approval. Such patients should continue to undergo frequent follow-up (i.e., at least once every 4 weeks ( $\pm 2$  weeks)) while eGFR  $\leq 15.0$  mL/min/1.73 m^2. Study drug may be re-started following acute dialysis, with Medical Monitor approval. Dialysis lasting at least 12 weeks will be confirmed as maintenance dialysis. Upon confirmation of maintenance dialysis, study drug should be discontinued.

Upon receipt of kidney transplant, study drug should be discontinued.

Following study drug discontinuation due to confirmation of maintenance dialysis or receipt of kidney transplant, patients should continue to be followed only for vital status and SAEs by phone or in person according to the planned contact schedule in Section 7.5 through their scheduled Week 112 visit date. See Section 8.5 for description of follow-up options following study drug discontinuation. Initiation of dialysis (acute and/or maintenance) and receipt of kidney transplant due to end stage kidney disease should be considered important medical events, and as such recorded as SAEs.

### 9.1.10 Monitoring Growth and Sexual Development in Adolescents

Growth and sexual development will be assessed through an evaluation of height, weight, and Tanner Staging. See the Study Reference Manual for details on the Tanner staging.

Body weight should be measured daily by patients/caregivers using a provided weighing scale. Weight and height will also be measured at all site visits, as outlined in Section 9.10.7. Patients should be instructed to inform the site if there is an observed weight loss of more than 3 pounds (1.4kg) in between clinic visits (Section 9.1.1).

The Medical Monitor will routinely evaluate both weight and height entered into the clinical database of adolescents and will inform the investigator to initiate further evaluation if there is a weight loss of  $\geq 5\%$  or lack of expected growth per growth charts.

Sexual maturity will be assessed by the investigator using Tanner Staging. If any abnormal patterns of sexual maturity are identified on evaluation of Tanner Staging, the Medical Monitor should be notified for additional discussion.

## **9.2. Description of Study Drug**

Bardoxolone methyl (RTA 402) drug product information is shown in [Table 6](#). Information about the placebo is shown in [Table 7](#).

**Table 6: Bardoxolone Methyl Drug Product Information**

Description	Bardoxolone methyl capsule (5 mg, 10 mg, 15 mg, 20 mg)
Ingredients	Bardoxolone methyl Methacrylic Acid – Ethyl Acrylate Copolymer (1:1), Type A Silicified Microcrystalline Cellulose Hydroxypropyl Methylcellulose Lactose Monohydrate Sodium Lauryl Sulfate Colloidal Silicon Dioxide Magnesium Stearate Gelatin capsules Titanium Dioxide (capsule pigment)
Route of Administration	Oral

**Table 7: Placebo Information**

Descriptiona	Placebo for bardoxolone methyl capsule (size #4, size #2, size #1, and size #0)
Ingredients	Silicified Microcrystalline Cellulose Lactose monohydrate Magnesium Stearate Gelatin capsules Titanium Dioxide (capsule pigment)
Route of Administration	Oral

a Placebo capsules are size matched to the corresponding active dose capsule

### 9.3. Concomitant Medications

#### 9.3.1. Excluded and Prohibited Medications

##### 9.3.1.1. Excluded Medications

Patients taking these medications or treatments will be ineligible for enrollment:

- Tolvaptan (patients on tolvaptan who have already enrolled under Version 2 of the protocol may remain in the trial);
- Somatostatin analogues
- Any other investigational drug or device as part of an interventional study within 30 days prior to Day 1;
- Chronic (> 2 weeks) immunosuppressive therapy, or need for corticosteroids, including therapies such as glucocorticoids, oncologic preparations, and anti-TNF $\alpha$  agents [e.g., infliximab (Remicade®), adalimumab (Humira®), certolizumab pegol (Cimzia®), etanercept (Enbrel®)] within 12 weeks prior to randomization. Glucocorticoid intra-articular injections, inhaled products, topical preparations, and nasal preparations are allowed.

If a patient takes an excluded medication during the study, the investigator should consult with the Medical Monitor immediately to discuss if there is need for study drug interruption or discontinuation.

### **9.3.1.2. Prohibited Medications**

Concomitant use with strong and moderate CYP3A4 inhibitors is prohibited, switching to alternate allowed medication should be considered. If a strong or moderate CYP3A4 inhibitor is medically necessary, discuss with Medical Monitor. Patients who are using these medications prior to screening should have a washout for at least 5-half-life's or 30 days whichever is longer.

Concomitant use with strong and moderate CYP3A4 inducers is prohibited, switching to alternate allowed medication should be considered. If a strong or moderate CYP3A4 inducers is medically necessary, discuss with the Medical Monitor. Patients who are using these medications prior to screening should have a washout for at least 5-half-life's or 30 days whichever is longer.

Concomitant use with chronic (> 2 weeks) immunosuppressive therapy (corticosteroids, including therapies such as glucocorticoids, oncologic preparations, and anti-TNF $\alpha$  agents [e.g., infliximab (Remicade®), adalimumab (Humira®), certolizumab pegol (Cimzia®), etanercept (Enbrel®)]) is prohibited.

Concomitant use with tolvaptan, somatostatin analogues, and any other investigational drug or device is prohibited. Concomitant dosing with prohibited medications is not allowed and will not be approved by the Medical Monitor. If a site becomes aware of a patient administering a prohibited medication, the Medical Monitor should be notified immediately to determine whether study drug should be permanently discontinued or whether an interruption is appropriate.

To minimize missing data and to maintain study integrity, patients who must take prohibited medications during the study should continue follow-up visits, even after study drug discontinuation, unless directed otherwise by the Medical Monitor. Certain prohibited medications (e.g., tolvaptan) will warrant termination from the study, due to the potential for the concomitant medication to confound the interpretation of study data.

Sites must avoid initiation of prohibited medications until all Off-Treatment assessments are completed (approximately 12 weeks following the patient's last dose of study drug).

If a patient permanently discontinues study drug and continues being followed in the study, the administration of a prohibited medication is no longer considered a protocol deviation after 12 weeks following the patient's last dose of study drug. Beginning 12 weeks after the patient's last dose, administration of a prohibited medication does not require input from the Medical Monitor.

Importantly, the administration of any medications listed in this section should be recorded in the concomitant medication page of the EDC independent of the patient's study drug status or duration since the patient's last dose of study drug, in order to ensure accurate interpretation of safety and efficacy data.

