### **8.5.1. Study Drug Discontinuation Criteria**

Study drug discontinuation refers to a patient's stopping administration of study drug permanently. Reasons for study drug discontinuation may include the following:

- Adverse event;
- Death;
- Lost to follow-up;
- Physician decision;
- Pregnancy;

- Protocol specified criterion met (Section 7.4, Section 9.1.1, Section 9.1.9, Section 9.3.1, Section 9.6.1, Section 9.8.3);
- Withdrawal by patient;

To maximize patient retention and minimize missing data, patients who discontinue study drug early are encouraged to remain active in the study and complete all future study visits and assessments, except PKs and ABPM, if applicable.

For patients who discontinue treatment prior to Week 100, see Section 8.3.3 for the required off-treatment assessments. After the off-treatment assessments, the patient will continue with follow-up assessments through Week 112. The collection of laboratory data and vital status through Week 112 (B) is important for trial integrity, and data may be obtained through in-person clinic visits or through home health visits.

See Section 9.10.16 for Adverse Event Collection following study drug discontinuation.

For patients who are unwilling to complete all future visits, the Week 108 visit is of paramount significance. Collecting Week 108 data for all randomized patients is essential for trial integrity.

For patients who discontinue study drug and are no longer willing to return for all scheduled study visits, a number of follow-up options are available and must be discussed with the patient thoroughly, including:

- Participation in follow-up procedures specified in the protocol by an in-home visit, where feasible;
- Reduced in-person visit schedule;
- Telephone contact only;
- Contact of alternative person(s) who has been designated in source records as being available to discuss the patient's medical condition;
- Non-direct follow-up of patient information including obtaining additional information from the patient's medical records (e.g., ESKD or death).

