### **9.6.1. Patient Unblinding**

Although bardoxolone methyl has no known antidote, under rare circumstances unblinding may be considered medically necessary.

The investigator is encouraged to contact the Medical Monitor to discuss situations in which he or she believes that the blind should be broken, but the investigator has the right to break the blind (e.g., in the event of a serious or life-threatening medical situation). If unblinding is required, the investigator will utilize the IWRS to perform the unblinding. If a study drug assignment is unblinded, the investigator must describe the event that required unblinding in the patient's source documents.

Patients must discontinue taking study drug if their treatment assignment has been unblinded to the investigator (or designee). Such patients must undergo the same study drug discontinuation procedures as those patients who discontinue taking study drug for other reasons. Following study drug discontinuation due to unblinding, patients should continue with study follow-up through their scheduled Week 112 visit date for vital status only.

Patient treatment assignments must not be unblinded in the case of an AE or SAE, except as described above.

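### Two protocol rules can end Week 108 eGFR collection, for tolvaptan starters and for unblinded patients, against sections 8.5.1 and 8.5.2 (minor, cheap to reconcile)

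*Protocol*

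**What the plan says.** Protocol 8.5.1 states the priority: "Collecting Week 108 data for all randomized patients is essential for trial integrity". It names sections 9.3.1 and 9.6.1 among the criteria for stopping study drug, and it has patients who stop early continue assessments through Week 112. Protocol 8.5.2 adds that, unless withdrawal of consent is documented, "patients should be followed for all protocol specified evaluations and assessments". It defines study termination as "stopping study follow-up, which includes study assessments, visits, and all contact with the site regarding the trial"; the reasons it lists are death, loss to follow-up and withdrawal of consent.

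Two other sections point the other way.

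- **Tolvaptan, Protocol 9.3.1.2.** The general rule is that "patients who must take prohibited medications during the study should continue follow-up visits", unless the Medical Monitor directs otherwise. The next sentence makes an exception, on the ground of confounding: "Certain prohibited medications (e.g., tolvaptan) will warrant termination from the study". The section then says that once a patient has been off drug for 12 weeks and "continues being followed in the study, the administration of a prohibited medication is no longer considered a protocol deviation".
- **Unblinding, Protocol 9.6.1.** "Such patients must undergo the same study drug discontinuation procedures" as other patients who stop, but after that "patients should continue with study follow-up through their scheduled Week 112 visit date for vital status only".

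SAP 8.4.1 analyses the Week 108 eGFR however long the patient has been off treatment. SAP 6.6.1 and 8.4.1 both say that missing values are not imputed.

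**The concern.** The primary analysis is declared on the ITT population and needs a Week 108 eGFR from each patient. Both rules act after randomisation and can remove that value from patients who are alive and have not withdrawn consent. Without imputation, such patients simply drop out of the ANCOVA.

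For tolvaptan, the loss could be related to outcome, because Protocol 7.3 ties its approval to rapidly progressing disease. For unblinding, which 9.6.1 calls rare, the documents suggest no link to eGFR, and the section gives no reason for stopping creatinine collection.

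The choice is also lopsided. A value that was collected can be set aside by an analysis rule, as SAP section 6 does for laboratory values after ESKD. A value that was never drawn cannot be recovered.

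**Working it through.** **1. The plan's own power.** Inputs from Protocol 12.1 and SAP 4.3.1: 850 patients, 1:1, difference 2.3, SD 12, two-sided alpha 0.05, two-sample t-test. The standard error is 12 × √(2/425) = 0.82. The exact noncentral t power at 425 per arm is 79.7%, which agrees with the stated figure of about 80%.

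**2. Reach of the unblinding rule.** If the usual discontinuation procedures apply, Protocol 8.3.3 gives visits at 21–25, 28–36, 56–64 and 84–92 days after the last dose. The Week 108 window for early discontinuers is study days 756–783 (SAP Table 4). With L the day of the last dose and L ≤ 699:

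- 12-week visits: L + 92 ≥ 756 gives L ≥ 664, so L = 664 to 699.
- 8-week visits: L + 64 ≥ 756 gives L ≥ 692, so L = 692 to 699.
- 3- and 4-week visits: L + 36 ≥ 756 would need L ≥ 720, so none.

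A Week 108 value therefore arises on 36 of 699 possible last-dose days (5.2%).

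**3. Reach of the tolvaptan rule.** The termination sentence has no time limit. The 12-week limit is an inference from the later paragraph on deviations. On that narrower reading, a patient who stops drug at Week 52 is clearly caught only until (364 + 84)/7 = Week 64. A completer has the Week 108 visits 56–64 days after the last dose, so a start after those visits costs no Week 108 value.

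**4. Effect on power.** The documents give no rates, so the shares lost are assumptions. The t-test is the one in step 1.

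| Assumed loss, one arm v the other | Patients analysed | Lost | Power |
|---|---|---|---|
| none | 425 / 425 | 0 | 79.7% |
| 1% v 1% | 421 / 421 | 8 | 79.3% |
| 1% v 2% | 421 / 416 | 13 | 79.1% |
| 3% v 5% | 412 / 404 | 34 | 78.1% |
| 3% v 10% | 412 / 382 | 56 | 76.9% |

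**5. Effect on the estimate.** If the lost patients have an eGFR change worse by d than the rest of their arm, then shift = (share lost on active − share lost on placebo) × d. An assumed upper end for d is the gap between the 4.8 per year decline in Protocol 5.1.1 and the 2.8 per year in Protocol section 5, over 108 weeks: (4.8 − 2.8) × 108/52 = 4.15. Neither rate describes tolvaptan starters. The lower end is d = 0.

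- 1-point imbalance: at most 0.01 × 4.15 = 0.04
- 2-point imbalance: at most 0.02 × 4.15 = 0.08
- 7-point imbalance: at most 0.07 × 4.15 = 0.29

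The sign depends on which arm loses more. Equal shares with equal d give zero. Against the standard error of 0.82, 0.04 is about 5% and 0.29 about 35%. Any effect of tolvaptan on values that are kept is ignored.

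**The case against.** The strongest defence is that the tolvaptan sentence is a deliberate, reasoned exception to a general rule and so not an oversight. The reasons for termination in 8.5.2 are introduced as included reasons, so the list may be open. Protocol 9.3.1.1 sends any use of an excluded medication, tolvaptan among them, to a discussion with the Medical Monitor and does not mention termination. Automatic loss is thus one reading. This stands in part: there is room for discretion. But 8.5.1 makes no exception for tolvaptan, and the defence does not reach unblinding, where confounding is not the stated reason.

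A reader might infer that most unblinded patients lose their Week 108 value. The day count does not show that: 36 of 699 is a share of dosing days, and it becomes a share of patients only if unblinding is spread evenly over time. The documents give no timing.

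A reader might also infer that the SAP has no way to handle eGFR after tolvaptan. The visible default includes any collected Week 108 value and sets aside only values after ESKD. Text around SAP 8.6 is redacted and may hold more. An analysis with and without such values is therefore a preference.

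Finally, much of the reporting exists. SAP 7.1 tabulates reasons for study termination and early discontinuers with eGFR through Week 108, and SAP 9.3 lists users of excluded medications. That stands. None of these gives the number of Week 108 values lost under each rule, by arm.

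**Conclusion.** The conflict is in the current text, and it is minor. Protocol 9.3.1.2 and 9.6.1 can end collection of the primary endpoint for patients whom 8.5.1 and 8.5.2 want followed, and without imputation those patients leave the primary ANCOVA.

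A reader might go further and conclude that the rules bias the treatment comparison. The documents do not support that. They give no rate of tolvaptan starts or unblinding, no difference by arm and no link to eGFR decline. The shares lost, the imbalance and the deficit in the working are all assumptions. Even the largest illustrated shift, 0.29, is about a third of one standard error, and the narrow reach of the tolvaptan rule argues for the smaller figures. The power figures take 850 patients with Week 108 data as the starting point and ignore losses from the study drug termination on 10 May 2023 (SAP section 2). As SAP 8.3 makes all significance levels nominal, what is left is mainly a question of accounting for who is missing and why.

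**What to change.** Reconcile Protocol 9.3.1.2 (both the termination sentence and the paragraph on use beyond 12 weeks) and 9.6.1 with 8.5.1 and 8.5.2. For data collection only, starting tolvaptan or being unblinded should not by itself end scheduled creatinine/eGFR collection, at minimum at Week 108. No view is taken on who may receive tolvaptan or be unblinded.

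Add to SAP 7.1 a by-arm count of Week 108 eGFR values lost under each of the two rules. An analysis with and without post-tolvaptan values is optional.

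The collection change needs a protocol amendment with IRB/EC approval (Protocol 15.5), re-consent (Protocol 9.10.1) and a few blood draws that are already scheduled. Its practical gain is now small. The count needs no protocol amendment, can be added before database lock, and uses recording of prohibited medications that Protocol 9.3.1.2 and 9.10.4 already require. It is the main remaining benefit.
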